## 3.4.2.11 Immunogenicity of T-Guard

ADA responses in the form of human anti-SPV-T3a-RTA and anti-WT1-RTA -antibodies will be evaluated in serum samples obtained at baseline and at Days 7, 14, 28, 90, and 180 following initiation of T-Guard treatment validated bioluminescence assays.

# 3.5 EXPLORATORY ENDPOINTS

## 3.5.1 Corticosteroid Dose

The steroid dose administered (measured in prednisone equivalent) at baseline, Days 28 and 56 will be described.

# 3.5.1.1 Near Complete Response (Near CR)

Near CR is defined as having stage 1 skin GVHD only (persistence of skin rash at less than 25% BSA) with a score of 0 in other target organs. The proportion of patients with a near CR will be evaluated at Day 7, 14, 28, and 56 post-initiation of T-Guard treatment. The OS rates at Day 180 will also be described for patients that attain a near CR or better and those who do not.

# 3.5.1.2 Discontinuation of Systemic Steroids

The proportion of patients that are free of systemic steroid therapy at Day 180 post- T-Guard initiation will be described.

# 3.5.1.3 Incidence of CMV Reactivation

The proportion of patients requiring new systemic treatment for a CMV PCR level per institutional practice (patients receiving only SoC viral prophylaxis will not be included in this assessment) for cytomegalovirus (CMV)-reactivation by Day 180 post-T-Guard initiation will be described.

# 3.5.1.4 Incidence of EBV-associated Lymphoproliferative Disorder

The proportions of patients with EBV-associated lymphoproliferative disorder and EBV reactivation requiring therapy with rituximab by Day 180 post-T-Guard initiation will be described.

# 3.5.1.5 Incidence of IMP-related Serious Adverse Events (SAEs)

SAEs that are deemed to be related to T-guard treatment will be summarized by type, frequency, and number of patients affected.

## 3.5.1.6 T-cell Subsets and NK-cells

The evolution of specific cell populations over the 180-day follow-up period and, in particular, T-Guard's effect in depleting targeted T cell and NK cell subsets as well as its impact on relevant non-target populations (B cells, monocytes and dendritic cells), will be evaluated.

The Phase 1/2 study showed that when using a pan T cell marker, there is no direct correlation between the T cell depletion patterns and clinical responses. This might be explained by the observed responses being induced by a shift in the composition of the T cell compartment towards more tolerogenic subpopulations, rather than by just grossly (but temporarily) reducing the total number of circulating T cells (and NK cells).

The flow cytometry analysis as proposed below, with a more refined and detailed set of markers, might help to further elucidate T-Guard's MoA and identify a surrogated biomarker for response.

Blood samples will be taken during the infusion week at Days 0, 2, 4, 6 (just prior to and 4 hours after each T-Guard infusion) and then subsequently at Days 14, 28, 56, and 180. These samples will be assessed by to measure the following cell populations: Inflammatory Monocytes & Dendritic Cells, Recent Thymic Emigrants, CD4+, CD8+ Naïve & Memory Cells, CD4+ T Regulatory Cells, NK Cells,  $\gamma\delta$  T Cells, and B cells.

# 3.5.1.7 GVHD-related biomarkers

Serum ST2 and Regenerating Family Member 3 Alpha (REG3α) concentrations and urine 3-Indoxyl Sulfate (3-IS) concentrations at baseline and at Day 7, 14, and 28 post-initiation of T-Guard treatment will be used to estimate the probability of NRM at Day 180 post-assessment for each patient, using the NRM risk model from (Major-Monfried, Renteria et al. 2018). The proportion of patients with high risk biomarker status (defined as estimated NRM greater than 0.29) will be described at each time point.

# 3.5.1.8 Patient Reported Outcomes (PROs)

Patient reported outcomes will be assessed using a subset of the PROMIS measures described in Appendix F. PROs will be assessed at baseline and Days 28, 56, and 180 post initiation of T-Guard treatment.

# 3.6 ENDPOINT REVIEW PROCESS

Upon completion of patient follow-up, an Endpoint Review Committee (ERC) will conduct an independent review of site-reported data on a key study endpoint, Day 28 aGVHD response, in order to determine the data to be presented in the primary manuscript and final analysis. This Committee will consist of members of the protocol team, including the Protocol Chairs, Protocol Officer, Operational Statistician, and Protocol Coordinator. Each patient's data will be reviewed by ERC clinicians. The adjudicated Day 28 aGVHD response data for each patient will be determined by consensus of the reviewers.

Data will be obtained from the relevant electronic case report forms (eCRFs) and source documents and will be provided to reviewers in a blinded manner with respect to treatment center and patient identifier. These data will be kept confidential and will not be discussed outside the Committee or presented in a public forum. The ERC charter will provide further details on the ERC membership and adjudication process.

# CHAPTER 4

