# 5.2 INTERIM ANALYSIS AND STOPPING GUIDELINES

## 5.2.1 Interim Analysis for Futility

This trial will include one interim analysis for futility. At the interim analysis, the number of Day 28 CRs will be compared to a futility boundary determined by Simon's two-stage minimax design comparing a null rate of 30% to an alternative rate of 50% with a one-sided type I error rate of 2.5% and 80% power. This is a non-binding stopping rule, in that the type I error rate will be controlled at 2.5% even if the rule is not followed exactly. If the number of CRs fails to exceed the boundary, the DSMB will be consulted on the appropriate course of action, including whether to declare futility and close the trial early.

The futility boundaries and operating characteristics of this design are displayed in Table 5- 2A. The interim analysis will be conducted when 21 patients are evaluable for Day 28 CR. If the number of CRs is 6 or below, the boundary is crossed. At the final analysis, the futility boundary is 20 CRs and efficacy is declared only if the observed number of CRs exceeds this boundary, i.e. the observed rate is at least 21/47 (44.6%).

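### Day 28 response is adjudicated after Day 180 follow-up with no stated masking to later outcomes, and the futility look and the final test would draw on different CR sources

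*Combined protocol and SAP*

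**What the plan says.** Section 3.6 sets the timing: "Upon completion of patient follow-up, an Endpoint Review Committee (ERC) will conduct an independent review of site-reported data on a key study endpoint". Follow-up runs to Day 180. The purpose of the review is stated as "in order to determine the data to be presented in the primary manuscript and final analysis"; the interim analysis is not mentioned.

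On membership: "This Committee will consist of members of the protocol team, including the Protocol Chairs, Protocol Officer, Operational Statistician, and Protocol Coordinator". The clinicians on the committee review each patient and settle the response by consensus. On what they see: "Data will be obtained from the relevant electronic case report forms (eCRFs) and source documents", and these "will be provided to reviewers in a blinded manner with respect to treatment center and patient identifier". No data cut-off is given. Masking to survival, to the later GVHD course or to the response assigned by the site is not mentioned. Some detail is deferred: "The ERC charter will provide further details on the ERC membership and adjudication process". The charter is not part of the documents.

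Section 5.2.1 says "The interim analysis will be conducted when 21 patients are evaluable for Day 28 CR". Six or fewer CRs cross the futility boundary, which is non-binding and leads to consultation with the DSMB. At the end, efficacy requires at least 21 CRs in 47 patients. Neither Section 5.2.1 nor Section 5.3 says whether the CRs counted are site-reported or adjudicated.

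**The concern.** Two features of the process are avoidable weaknesses.

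First, a Day 28 classification made after Day 180 can be influenced by what happened in between. CR under Section 3.1 is stage 0 in every evaluable organ with no intervening systemic therapy. Most of that is objective, but some calls need judgement. Appendix C separates upper GI stage 0 from stage 1 by intermittent versus persistent symptoms, and Section 2.5.8.2 excludes a resumed prophylaxis agent from counting as a second agent. A reviewer who knows that a patient later flared, was rescued or died may lean one way on such a call. There is no control arm in which the same leaning would appear, and the efficacy decision turns on 20 versus 21 CRs.

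Second, a Simon design assumes one response variable at both stages. If the first-stage count is site-reported and the final count adjudicated, the stopping probabilities in Table 5-2A and the 80% power describe a procedure slightly different from the one that will be run.

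**Working it through.** **Plan's own figures (Sections 5.1.5 and 5.2.1, Table 5-2A).** Inputs: null rate 30%, alternative 50%, n1 = 21 with boundary 6, N = 47 with boundary 20. Write b(x; n, p) for the binomial probability.

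- Futility signal, P(X1 ≤ 6; 21, p): 55.1% at p = 0.30 and 3.9% at p = 0.50. Both match Table 5-2A.
- Efficacy with futility followed, Σ over x = 7 to 21 of b(x; 21, p) · P(Bin(26, p) ≥ 21 − x): 2.27% at 0.30 and 80.0% at 0.50.
- Efficacy with futility ignored, P(X ≥ 21; 47, p): 2.35% at 0.30 and 80.9% at 0.50.
- A search for the minimax design returns the same 6/21 and 20/47. The design reproduces.

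**Which data the interim can use.** Inputs: 47 patients over 365 days (Section 5.1.1), uniform accrual (the assumption behind the safety simulations in Section 5.2.2), Day 28 evaluation and Day 180 follow-up.

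- Spacing: 365/47 = 7.77 days.
- 21st patient starts at 21 × 7.77 ≈ day 163 and is evaluable at 163 + 28 = day 191.
- Patients with 180 days of follow-up by then started by day 191 − 180 = 11, and 11/7.77 ≈ 1.4, so one patient.
- If completion of follow-up means all patients, adjudication starts near day 365 + 180 = 545.

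On either reading the futility count is almost wholly unadjudicated.

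**Interim: effect of a miscount of one.** One CR missed by the sites means that 7 or fewer true CRs trigger the signal.

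- Futility signal at a true 50%: P(X1 ≤ 7; 21, 0.5) = 9.5%, up from 3.9%.
- Power if the rule is followed: 77.7%, down from 80.0%.
- One CR overcounted (5 or fewer true CRs trigger): the signal at a true 30% falls from 55.1% to 36.3%.
- Type I error cannot exceed the 2.35% that applies when futility is ignored, whichever source the interim uses.

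**Final: effect of net reclassification, applied in every trial.**

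- One net upgrade to CR, P(X ≥ 20; 47, 0.3): type I error 4.58%, against 2.35%.
- Two net upgrades: 8.31%.
- One net downgrade, P(X ≥ 22; 47, 0.5): power 72.0%, against 80.9%.
- As a per-patient error (assumed; the documents give no rate): if 2% of true non-CRs are called CR, the apparent null rate is 0.30 + 0.70 × 0.02 = 0.314 and type I error is 3.8%. At 5% the rate is 0.335 and type I error is 7.3%.

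**How often the count sits at the edge.** P(20 or 21 CRs of 47) is 3.5% at a true 30%, 20.4% at 40% and 15.9% at 50%. An upgrade changes the decision only at exactly 20: 4.58 − 2.35 = 2.2% at a true 30%. A downgrade changes it only at exactly 21: 80.9 − 72.0 = 8.9% at a true 50%.

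**The case against.** A reader might infer from Section 3.6 that the committee will judge CR knowing each patient's survival and the running site-reported total. The documents do not say so. Reviewers receive the relevant forms and source documents for one endpoint, and the pending charter may restrict them further. What stands is that the protocol does not prevent such knowledge, and that members of an open-label trial's protocol team could have it from other sources.

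A reader might also infer that a site-reported interim inflates type I error. It does not: the rule is non-binding, and the final test alone controls the error. Even a systematic undercount of one costs only about 2 points of power.

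The endpoint is also firmer than most response scales. Staging uses bilirubin, stool-output and rash thresholds recorded at the Day 28 visit, and later events are not part of the definition. This limits the room for bias but does not remove it. Any 47-patient rule has an edge at one count, so the probabilities of 20 or 21 describe fragility and do not measure bias. At the 30% null, where a false claim would arise, that probability is only 3.5%.

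Finally, adjudicating earlier has its own risk: the same reviewers could keep an informal count during accrual. That is fair, and the fix has to deal with it.

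**Conclusion.** The point holds as a worthwhile, inexpensive improvement. As written, Day 28 response is adjudicated after Day 180 with stated masking only to "blinded manner with respect to treatment center and patient identifier". By timing, the futility look would use almost wholly site-reported CR while the final test uses adjudicated CR. The interim source is an inference from the accrual plan, since the protocol does not name it.

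The consequence at the interim is limited to a wrong stop or continue signal. At the final analysis, a shift of a single patient is enough to take type I error above the 2.5% limit or to cut power by about 9 points. These are sensitivities to an assumed shift. The documents give no misclassification rate, and nothing in them shows that late adjudication would change any call. Nor is Day 28 CR the only efficacy endpoint: it is the only primary one, with duration of CR and overall survival as key secondary endpoints.

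**What to change.** - **Section 3.6 and the ERC charter:** limit the review package to staging and systemic-therapy data up to and including the Day 28 visit. Mask reviewers to later outcomes and to the site-assigned response.
- **Timing:** complete adjudication of the first 21 patients before the futility look, then adjudicate the rest as a second batch. Do not tabulate totals for the committee.
- **Sections 5.2.1 and 5.3:** name adjudicated CR as the source for both tests, and report site-reported CR as a sensitivity analysis.

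N = 47 and the 6/21 and 20/47 boundaries stay as they are, as do the reviewers and the data collected. The costs are wording changes, a charter edit and a possible short wait at the interim while source documents from about 20 centers are gathered. Reviewers could still count their own first-batch decisions informally. Two batches limit this better than continuous review, but do not exclude it.

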# 4 PATIENT ENROLLMENT AND EVALUATION

# 4.1 APPROACHING PATIENTS, ELIGIBILITY SCREENING, AND OBTAINING CONSENT

Patients with SR-aGVHD will be approached as soon as possible after diagnosis. Patients at least 18 years of age and willing to participate in the trial will sign an Institutional Review Board (IRB) approved ICF, and eligibility for enrollment will be further evaluated. For patients at least 12 but less than 18 years of age and willing to participate, assent will be obtained in addition to parent or guardian consent. The process of obtaining informed consent must comply with applicable ICH GCP E6 guidelines as implemented in US guidelines, GCP guidelines and national regulatory requirements.

## 4.2 ENROLLMENT

Patients will be enrolled onto the study using Advantage eClinical. The following procedures shall be followed:

- 1. An authorized user at the clinical center completes the initial screening by entering patient demographics and Segment A information (consent date, inclusion/exclusion criteria) on the Eligibility Form.
- 2. If the patient is eligible, a patient ID number is generated.

If a connection is interrupted during an enrollment session, the process is completely canceled and logged. A backup manual enrollment system will also be available to provide for short- term system failure or unavailability.

## 4.2.1 Treatment]

Treatment should be initiated as soon as possible after enrollment. A maximum of 72 hours (3 days) is allowable.

#### 4.3 STUDY MONITORING

#### 4.3.1 Follow-up Schedule

The Follow-up Schedule for scheduled study visits is outlined in Table 4.1. The timing of followup visits is based on the date of first T-Guard infusion (Day 0) A detailed description of each of the forms and the procedures required for forms completion and submission can be found in the Data Management Handbook and User's Guide.

#### Table 4.1: Follow-up Schedule

Assessment Time	Target Day  (Days Post-Enrollment)
1 week	7 days
2 weeks	14 days
3 weeks	21 days

Assessment Time	Target Day  (Days Post-Enrollment)
4 weeks	28 days
5 weeks	35 days
6 weeks	42 days
7 weeks	49 days
8 weeks	56 days
10 weeks	70 days
90 days	90 days
6 months	180 days

Target day range =  $\pm$ 3 days for Day 7 (subsequent visits through Day 56 must be scheduled weekly and within  $\pm$ 3 days of target date). Target day range  $\pm$ 14 days for Days 70, 90, and 180

**Criteria for Forms Submission**: Criteria for timeliness of submission for all study forms are detailed in the Data Management Handbook and User's Guide. Forms that are not entered in Advantage eClinical within the specified time will be considered delinquent. Transplant Centers can view past due forms via Advantage eClinical. A missing form will continue to appear until the form is entered into Advantage eClinical, or until an exception is granted and entered into the Missing Form Exception File, as detailed in the Data Management Handbook and User's Guide.

**Reporting Patient Deaths:** The Recipient Death Information must be entered into Advantage eClinical within 24 hours of knowledge of a patient's death even if the cause of death is unknown at that time. Once the cause of death is determined, the form must be updated.

**Center for International Blood and Marrow Transplant Research (CIBMTR) Data Reporting:** Centers participating in BMT CTN trials must register pre and post-transplant outcomes on all consecutive HCTs done at their institution during their time of participation to the CIBMTR. Registration is done using procedures and forms of the Stem Cell Transplant Outcomes Database (SCTOD). (Note: Federal legislation requires submission of these forms for all US allotransplant recipients.) CIBMTR post- transplant Report Forms must continue to be submitted for all patients enrolled on this trial. Long-term follow-up of patients on this study will continue through routine CIBMTR mechanisms.

## 4.3.2 Assessments

Assessment and/or reporting of the following is required for patients enrolled on this study. All assessments are considered standard-of-care unless identified below by "\*" below. Assessments indicated by "\*" are for research purposes.

#### Prior to Enrollment

The following pre-enrollment assessments must be completed prior to enrolling the patient in Advantage eClinical and within the designated timeframe listed below.

1. Complete acute GVHD staging and grading information including assessments of rash, diarrhea, nausea/vomiting, and bilirubin, within 24 hours prior to enrollment. Biopsy results of involved tissue, if performed as SoC, should also be reported.

- 2. Albumin, platelet count, and CK level within 24 hours prior to enrollment
- 3. Complete blood count (CBC) with differential within 24 hours prior to enrollment
- 4. Pregnancy test (urine or serum) for females of child-bearing potential within 30 days prior to enrollment

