patients with severe hypoalbuminemia, with an albumin of less than or equal to 1 g/dl, a creatine kinase (CK) level greater than 5 times the upper limit of normal; patients with an uncontrolled infection (infections are considered controlled if appropriate therapy has been instituted and, at the time of enrollment, no signs of progression are present). Patients with evidence of relapsed, progressing, or persistent malignancy, or with evidence of minimal residual disease requiring withdrawal of systemic immune suppression are not eligible for this trial. Patients with known hypersensitivity to any of the components murine monoclonoal antibodies (mAb), or Recombinant Ricin Toxin A-chain (RTA), or have received more than one allo-HSCT, or who have known human immunodeficiency virus infection are also excluded from this trial. Pregnant or breastfeeding females, and females of childbearing potential unwilling to use effective birth control from start of treatment until 30 days after the last infusion of T-Guard are not eligible to participate. Male patients who are sexually active and unwilling to use effective birth control from start of treatment until 65 days after the last infusion of T-Guard are not eligible.

- Interim Analysis: This trial will include one interim analysis for futility after 21 patients become evaluable for the primary endpoint. There will be no interim analyses for efficacy.
- Treatment Description:Patients will receive 4 doses of T-Guard treatment,
administered intravenously as four 4-hour infusions at least two
calendar days apart. Each dose consists of 4 mg/m² Body
Surface Area (BSA).

Accrual Objective: The target accrual is 47 patients initiating T-Guard treatment.

Accrual Period: Approximately 1 year is expected for accrual.

Study Duration:Patients will be followed for 180 days for a total study duration
of approximately 1.5 years.

Safety Monitoring:The rates of overall mortality and CTCAE Grade 4 or higher
capillary leak syndrome (CLS) at Day 30 post treatment
initiation will be monitored separately using sequential
probability ratio tests (SPRT) for binary data. The SPRTs will
contrast a mortality rate of 15% vs. a 30% rate and a Grade 4
or higher CLS rate of 5% vs. a 15% rate.

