# 2.4.2 Exclusion Criteria

Patients will be excluded from study entry if they meet any of the following exclusion criteria:

- 1. Patients who have been diagnosed with overlap syndrome, that is, with any concurrent features of cGVHD.
- 2. Patients requiring any of the following: mechanical ventilation, vasopressor support, or hemodialysis.
- 3. Patients who have received any systemic treatment, besides steroids, as upfront treatment of aGVHD OR as treatment for SR-aGVHD.
- 4. Patients who have severe hypoalbuminemia, with an albumin of less than or equal to 1 g/dl.
- 5. Patients who have a CK level of greater than 5 times the upper limit of normal.
- 6. Patients with uncontrolled infections. Infections are considered controlled if appropriate therapy has been instituted and, at the time of enrollment, no signs of progression are present. Progression of infection is defined as hemodynamic instability attributable to sepsis, new symptoms, worsening physical signs or radiographic findings attributable to infection. Persisting fever without other signs or symptoms will not be interpreted as progressing infection.
- 7. Patients with evidence of relapsed, progressing or persistent malignancy.
- 8. Patients with evidence of minimal residual disease requiring withdrawal of systemic immune suppression.
- 9. Patients with known hypersensitivity to any of the components murine monoclonal antibodies (mAb) or Recombinant Ricin Toxin A-chain (RTA).
- 10. Patients who have received more than one allo-HSCT.
- 11. Patients with known human immunodeficiency virus infection.
- 12. Female patients who are pregnant, breast feeding, or, if sexually active and of childbearing potential, unwilling to use effective birth control from start of treatment until 30 days after the last infusion of T-Guard.
- 13. Male patients who are, if sexually active and with a female partner of childbearing potential, unwilling to use effective birth control from start of treatment until 65 days after the last infusion of T-Guard.
- 14. Patients with any condition that would, in the investigator's judgment, interfere with full

participation in the study, including administration of study drug and attending required study visits; pose a significant risk to the patient; or interfere with interpretation of study data.

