# 2.5.6 T-Guard Discontinuation

T-Guard treatment must be completed within 14 days of the first study drug dose. Patients who have missed doses may re-start T-Guard provided it is within the 14-day treatment window.

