#### Baseline Assessments

Baseline assessments listed below must be completed post-enrollment and within 24 hours prior to the first dose of study therapy unless otherwise specified.

- 1. Karnofsky or Lansky Performance Status (may be completed pre- or post-enrollment)
- 2. Baseline patient-reported outcome measures (Appendix F)
- 3. Peripheral blood for EBV and CMV viral load (within 72 hours prior to first T-Guard dose)
- 4. Peripheral blood\* for EBV, CMV-specific and alloreactive T-cells (See Appendix B)
- 5. CBC with differential and platelet count\* (must be collected at the same time as the 30mL peripheral blood for alloreactive T-cells)
- Peripheral blood\* for humoral response (ADA) and immunophenotyping (See Appendix B)
- 7. Peripheral blood\* and urine sample\* for GVHD biomarker testing (See Appendix B)
- 8. Recording of all systemic immune suppressive therapy (as appropriate: tacrolimus, cyclosporine, etc.), as well as topical agents
- 9. History and physical exam including height and weight, patient disease/transplantation baseline variables (may be completed pre- or post-enrollment but must be within 7 days prior to first T-Guard dose)

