#### Table 4.2: Assessment Schedule

	Pre- Enrollment	Baseline 		of T- fusio		ard				C	ays	Post	Initia	tion c	of T-G	luard	
	Base	line	0	2	4	6	7	14	21	28	35	42	49	56	70	90	180
Acute GVHD evaluation, including bilirubin	х		х	х	х	х	х	х	х	х	х	х	х	х	х	х	Х
Chronic GVHD evaluation										Х				Х		Х	Х
Recording of all systemic immune suppression, including steroid dose		х					х	x	x	x	х	x	x	x	x	х	х
History and physical exam		Х															
CBC with differential		X 	Х	Х						X 				Х		Х	X 
Platelet count	Х	X 	Х	Х		Х				X 				Х		Х	X 
Albumin	Х		Х	Х	Х	Х				Х				Х		Х	Х
CK levels 	Х																
Pregnancy test (if applicable)	Х																
Karnofsky/Lansky performance status		х								х				х		х	х
	Pre- Enrollment	Baseline 		of T- fusio		ard				D	)ays	Post	Initia	tion c	of T-G	luard	
	Base	line	0	2	4	6	7	14	21	28	35	42	49	56	70	90	180
Peripheral blood for CMV and EBV viral load		х								х							х
Peripheral blood for EBV, CMV-specific and alloreactive T- cells 		x								х							х
Pharmacokinetics 			Х	Х	Х	Х											
Peripheral blood for ADA		Х					Х	Х		Х						Х	Х
Peripheral blood for GVHD biomarkers REG3α and ST2		х					Х	х		х							
Peripheral blood for immunophenotyping 		х	х	x	х	х		x		х				х			х
Urine sample for GVHD biomarker 3-IS		х					Х	х		х							
Vital signs (temperature, pulse, respiratory rate, blood pressure) 			х	x	х	x											
AE/SAE assessment 			x	x	x	х	х	x	x	х	х	х	х	x	х	х	х
Toxicity assessment														x	x	х	х
Patient-reported outcomes: PROMIS		х								х				х			Х
Infection monitoring	Re	eporting of	infectio	ons a	at tir	ne d	of occ	urre	nce	from	n time	e of e	nrollr	nent	throu	gh Da	y 180
Primary disease relapse reporting		Reporting c														-	-

Baseline assessments must be completed post enrollment and within 24 hours prior to the first dose of study treatment unless otherwise specified.

If patients experience muscle pain, then a serum CK should be performed.

The CBC with differential and platelet count must be taken at the same time as the peripheral blood is drawn for EBV, CMV-specific and alloreactive T-cells at baseline, day 28, and day 180.

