## 4.4.5 Procedure in Case of Pregnancy

If a female patient becomes pregnant during the study dosing period or within 90 days from the last dose of study drug, the investigator should report the information through an expedited AE reporting system via Advantage eClinical. The expected date of delivery or expected date of the end of the pregnancy, last menstruation, estimated conception date, pregnancy result, neonatal data and other related information will be requested. If a patient becomes pregnant during the study dosing period, the investigational product will be discontinued.

The investigator will follow the medical status of the mother, as well as the fetus, as if the pregnancy is an SAE and will report the outcome. Additional information regarding the outcome of a pregnancy (which is categorized as an SAE) is mentioned below.

- "Spontaneous abortion" includes miscarriage, abortion and missed abortion
- Death of an infant within 30 days after birth should be reported as an SAE regardless of its relationship with the study drug
- If an infant dies more than 30 days after birth, it should be reported if a relationship between the death and intrauterine exposure to the study drug is judged as "possible" by the investigator
- In the case of a delivery of a living newborn, the "normality" of the infant is evaluated at the birth
- Unless a congenital anomaly is identified prior to spontaneous abortion or miscarriage, the embryo or fetus should be assessed for congenital defects by visual examination

Information will be collected at the time of delivery/birth and 180 and 360 days after birth.

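### The only required pregnancy test may be up to 33 days old at first infusion, and no required measure covers the interval before dosing

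*Combined protocol and SAP*

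**What the plan says.** Exclusion criterion 12 (Section 2.4.2) excludes female patients who are pregnant. It also excludes those who, if sexually active and of childbearing potential, are "unwilling to use effective birth control from start of treatment until 30 days after the last infusion of T-Guard". The synopsis gives the same contraception period.

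The supporting test appears in Section 4.3.2 under Prior to Enrollment: "Pregnancy test (urine or serum) for females of child-bearing potential within 30 days prior to enrollment". On the interval from enrollment to first infusion, Section 4.2.1 says: "A maximum of 72 hours (3 days) is allowable".

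The next set of checks is introduced in these words: "Baseline assessments listed below must be completed post-enrollment and within 24 hours prior to the first dose of study therapy unless otherwise specified". Nine items follow, and a pregnancy test is not one of them. The list for each infusion does not include one either. In Table 4.2 the pregnancy test has a single mark, in the pre-enrollment column.

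On the length of dosing, Section 2.5.6 says: "T-Guard treatment must be completed within 14 days of the first study drug dose". Section 4.4.5 covers reporting, follow-up and discontinuation of the product once a pregnancy is known, but schedules no test to find one.

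**The concern.** An exclusion criterion is only as good as the check behind it. Here the check may predate first dose by more than a month, while the contraception condition starts at first dose. A patient can test negative, conceive before treatment starts, and be dosed with a ricin-based immunotoxin although every scheduled step was done on time.

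The long window also sits oddly with how patients enter the trial. Two of the routes to steroid-refractory status are defined by 3 or 7 days of steroid treatment, and Section 4.1 has patients approached as soon as possible after diagnosis. A test taken 30 days before enrollment may therefore predate the condition that qualifies the patient. The population includes females of childbearing potential and extends down to age 12.

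What is at stake is fetal exposure and compliance with criterion 12, not the estimate of the Day 28 complete response rate.

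**Working it through.** The plan states no figure for the age of the test at dosing, so there is none to reproduce. It follows by adding the permitted windows.

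**Inputs**
- Test to enrollment: at most 30 days (Section 4.3.2, Prior to Enrollment).
- Enrollment to first infusion: at most 72 hours = 3 days (Section 4.2.1).
- First to last infusion: Day 6 on the planned schedule (Section 2.5.4), at most 14 days if delayed (Section 2.5.6).
- Start of the contraception condition: start of treatment (Section 2.4.2 and synopsis).

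**Maximum age of the only required test**
- At first infusion: 30 + 3 = 33 days.
- At a fourth infusion given on Day 6: 33 + 6 = 39 days.
- At a last infusion given at the 14-day limit: 33 + 14 = 47 days.

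**Is the interval covered by anything required?**
- Contraception: no. The condition starts at first infusion, so the whole interval of up to 33 days precedes it.
- Repeat test at baseline, on infusion days or elsewhere in Table 4.2: none.
- History and physical examination: required within 7 days before first dose, but the item does not name pregnancy.
- Section 4.4.5: acts only after a pregnancy is known.

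**Effect of moving the test**
- Into the baseline set: at most 24 hours old at first infusion, so the result meets the start of the contraception condition to within a day.
- Into the 24-hour pre-enrollment window used for albumin, platelets, CK and blood count: 24 h + 72 h = 96 h, or up to 4 days old at first infusion. This shortens the gap but does not close it.

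**The case against.** The strongest case on the other side is that nothing here is contradictory. A 30-day test window and contraception from start of treatment can both be followed, and a tighter window is a preference. That is correct: this is a design choice that could be better, not an inconsistency. The comparison with the 24-hour entry laboratory checks is also only suggestive. Albumin and CK are eligibility thresholds that also govern withholding of doses, so there is a separate reason to time them to current status.

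A reader might infer that a pregnancy in this interval would inevitably go unnoticed. The documents do not support that. Criterion 12 bars any pregnant patient, not only one with a positive test. A history and physical examination falls within 7 days before dosing, and criterion 14 lets the investigator exclude a patient at significant risk. Section 4.3.2 also classes the test as standard of care, so a site may repeat it unprompted. What stands is narrower: none of these requires a test, or contraception, between the scheduled test and first dose.

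A reader might also infer that pregnancies in partners of male patients go unreported, because criterion 13 requires male contraception for 65 days after the last infusion while Section 4.4.5 opens with "If a female patient becomes pregnant during the study dosing period or within 90 days from the last dose of study drug". That does not hold as a defect. Section 4.4.4 makes pregnancy a Special Situation, reportable within 24 hours of knowledge and not restricted to female patients. At most, Section 4.4.5 could be clarified to match.

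Finally, the likelihood is low: these patients have recently had an allogeneic transplant and are on high-dose steroids. That limits the importance of the point but does not answer it.

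**Conclusion.** The point holds as a minor, inexpensive safety improvement. The only required pregnancy test may be up to 33 days old at first infusion, and no required measure in that interval would prevent or detect a pregnancy.

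The 33 days assumes that both windows are used in full. The documents give no usual interval and no conception rate, so the expected number affected cannot be calculated. With 47 treated patients, of whom only some would be of childbearing potential, it is likely to be small. The primary endpoint, the error rates and the analysis population are unaffected. The case for acting is a rare but serious and avoidable event set against a negligible cost.

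**What to change.** Reconcile Sections 2.4.2, 4.2.1 and 4.3.2 (Prior to Enrollment and Baseline Assessments) with Table 4.2, by moving the same single test from the pre-enrollment list to the existing baseline set, due after enrollment and within 24 hours before first dose. In Table 4.2 the mark moves from the pre-enrollment to the baseline column.

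Cost: wording in two places. No visit is added, the test may be done on urine or serum, and both blood and urine are already collected at baseline. Sample size and analysis do not change.

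Downsides to accept:
- A result already on file from an earlier date cannot be reused.
- A positive result would arrive after enrollment. Section 2.5.9 allows an enrolled but untreated patient to be replaced, and Section 5.1 continues enrollment until 47 patients are treated, so the cost is one extra enrollment.
- A test close to dosing may still miss a very recent conception, so the gap is narrowed rather than eliminated.

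If the sponsor prefers to keep the 30-day window, the protocol should give the reason.
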